Appendix F Child-Pugh Score for Cirrhosis Mortality

Factor	1 point	2 points	3 points
Total bilirubin	<2 mg/dl or 34 µmol/L	2-3 mg/dl or 34-51 μmol/L	>3 mg/dl or 51 μmol/L
Serum albumin	>3.5 g/dl	2.8-3.5 g/dl	<2.8 g/dl
PT-INR	< 1.7	1.7- 2.2	>2.2
Ascites	Absent	Slight	Moderate
Hepatic encephalopathy	None	Grade 1-2	Grade 3-4
Total points	5-6	7-9	10-15
Class	A	В	C

INR: international normalized ratio; PT: prothrombin time.

Confidential Page 78 of 78

1 LIST OF ACRONYMS AND ABBREVIATIONS

Abbreviation	Term
ADA	Anti-Drug Antibody
AE	Adverse Event
AESI	Adverse Event of Special Interest
ALT	Alanine Aminotransferase
AST	Aspartate Aminotransferase
ATC	Anatomical Therapeutic Chemical
AUC	Area under the drug concentration time curve
BMI	Body Mass Index
BOR	Best Overall Response
CI	Confidence Interval
CL	Systemic Clearance
C_{max}	Maximum concentration
C _{min}	Minimum concentration
CR	Complete Response
CSR	Clinical Study Report
CTCAE	Common Terminology Criteria for Adverse Events
DCR	Disease Control Rate
DLT	Dose-Limiting Toxicity
DOR	Duration of Response
ECG	Electrocardiogram
ECOG	Eastern Cooperative Oncology Group
eCRF	electronic Case Report Form
eDISH	evaluation of Drug-Induced Serious Hepatotoxicity
HCC	Hepatocellular Carcinoma
HR	Hart Rate
ICH	International Conference on Harmonization
irAE	Immune-related Adverse Event
IV	Intravenous
K-M	Kaplan-Meier
MedDRA	Medical Dictionary for Regulatory Activities

NCI	National Cancer Institute
NE	Non-Evaluable
ORR	Objective Response Rate
OS	Overall Survival
PD	Progressive Disease
PD-1	Programmed Cell Death Protein 1
PD-L1	Programmed Cell Death Protein 1 Ligand 1
PFS	Progression Free Survival
PI	Principal Investigator
PK	Pharmacokinetic(s)
PR	Partial Response
PT	Preferred Term
QTcF	QT Interval Corrected Using Fridericia's Formula
RECIST	Response Evaluation Criteria in Solid Tumors
SAP	Statistical Analysis Plan
SD	Stable Disease
SDV	Source Data Verification
SOC	System Organ Class
TEAE	Treatment-Emergent Adverse Event
t _{max}	Time to Reach Maximum Drug Concentration
t½	Terminal Elimination Half-Life
ULN	Upper Limit of Normal
USA	United States of America
Vd	Volume of Distribution

Confidential Page 8 of 30

AMENDMENT FROM PREVIOUS VERSION

This is the second version of the SAP for Phase 2 study.

2 INTRODUCTION

The objective of this Statistical Analysis Plan (SAP) is to provide a comprehensive and detailed description of the strategy, rationale, and statistical techniques that will be used for analysis of Phase 2 data in order to address the primary and secondary objectives of the dose expansion part of the protocol C-500-01, titled: "Phase 1/2, Open-Label, Multicenter Study to Evaluate the Safety, Pharmacokinetics, and Pharmacodynamics of an Anti–CTLA-4 Human Monoclonal Antibody (AGEN1884) in Subjects with Advanced or Refractory Cancer and in Subjects who have Progressed During Treatment with a PD-1/PD- L1 (programmed cell death protein 1/programmed cell death protein 1 ligand 1) Inhibitor as their Most Recent Therapy."

This document has been prepared based on the protocol amendment 9, dated 26 November 2019 and the Case Report Form dated 14 January 2020. The statistical analyses adhere to principles specified in E9 guidance "Statistical Principles for Clinical Trials" of International Conference on Harmonisation (ICH). This SAP does not include pharmacokinetic (PK) analysis. The PK analysis will be described in a separate PK SAP.

3 STUDY DESIGN OVERVIEW

[figure not shown]
3.1 Overall Study Design

This is an open-label, Phase 1/2, multicenter study to evaluate the safety, PK, and pharmacodynamics, and activity of an anti–CTLA-4 human monoclonal antibody (AGEN1884) in subjects with advanced or refractory cancer. The Phase 1 portion of the study has been completed and contained a 3+3 dose escalation phase evaluating AGEN1884 at 0.1, 0.3, 1, 3, and 6 mg/kg dose levels, and an expansion phase at 1 mg/kg and 3 mg/kg. Dose levels >6mg/kg were not planned.

The Phase 2 portion of the study includes subjects who have progressed during treatment with an approved or investigational PD-1/PD-L1 inhibitor as their most recent therapy (2-6 weeks prior to first dose of study drug). The dose for the Phase 2 portion of the study was based on clinical data from the Phase 1 portion evaluating AGEN1884 as monotherapy. At the time of the protocol amendment 9, based on data from the Phase 1 dose escalation, 1 mg/kg was chosen as the starting dose for Phase 2.

The study design is depicted in Figure 1.

Figure 1: Study Design

* Additional subjects may be enrolled in Phase 2 to either the hepatocellular carcinoma (HCC) or non-HCC populations as necessary to ensure that 20 subjects are evaluable for additional PK assessments.

AGEN1884 will be administered intravenously (IV) for each cycle (3 weeks) as a 60-min (- $10/\pm20$ min) infusion. Infusions will be followed immediately by a 15-min saline flush of the IV line. Treatment will be administered every 3 weeks for the first 4 cycles. At the 12-week evaluation timepoint, subjects may continue to receive AGEN1884 every 3, 6, or 12 weeks (\pm 7 days) for a maximum duration of 1 year of treatment, provided they were not diagnosed with progressive disease and were tolerating the study drug.

3.2 Sample Size

Overall, there will be approximately 100 subjects enrolled in Phase 1 and Phase 2 of this study. After safety is established in the 1 mg/kg and 3 mg/kg cohorts, additional subjects will be enrolled into those dose levels to support the objectives and expand the number of correlates available for evaluation. The Phase 2 population will include up to 60 subjects who have progressed during treatment with an approved or investigational PD-1/PD-L1 inhibitor as their most recent therapy (2-6 weeks prior to first dose of study drug) with a subpopulation to include approximately 20 subjects with advanced HCC and approximately 40 non-HCC subjects.

These sample sizes are not based on inferential statistics.

Confidential Page 10 of 30

3.3 Randomization and Blinding

This is an open-label Phase 1/2 study. Subjects are not randomized to study treatment.

4 STUDY OBJECTIVES AND ENDPOINTS

4.1 Primary Objective

- To evaluate the safety, tolerability, and dose-limiting toxicities (DLTs) of AGEN1884 in subjects with advanced or metastatic cancer (solid tumors or lymphoma), including but not limited to carcinoma, sarcoma, or melanoma (Phase 1); and to evaluate the safety and tolerability of AGEN1884 in subjects who have progressed during treatment with a PD-1/PD-L1 inhibitor as their most recent therapy (Phase 2).
- To characterize AGEN1884 pharmacokinetics (PK).

4.2 Secondary Objectives

- To evaluate the preliminary efficacy of AGEN1884 by assessing objective response rate (ORR), disease control rate (DCR), and duration of response (DOR) per Response Evaluation Criteria in Solid Tumors (RECIST) Version 1.1.
- To evaluate the preliminary efficacy of AGEN1884 by assessing progression-free survival (PFS) and overall survival (OS).

4.3 Exploratory Objectives

- To explore biomarkers that may predict pharmacologic activity or response to AGEN1884.
- To characterize the effect of AGEN1884 on tumor tissue obtained post-treatment, if available.

4.4 Primary Endpoints

- Safety and tolerability will be assessed by monitoring the frequency, duration, and severity of drug-related adverse events; by completing physical examinations; by evaluating changes in vital signs and electrocardiogram (ECG); through clinical evaluations; and laboratory blood and urine sample evaluations.
- PK parameters to be estimated and reported may include, but may not be limited to, maximum drug concentration at steady-state (C_{max-ss}), minimum drug concentration at steady state (C_{min-ss}), area under the drug concentration-time curve within time span t1 to t2 at steady-state (AUC_{(t1-t2)-ss}), area under the drug concentration-time curve from time of dosing to time of last observation (AUC_(0-t)), area under the drug concentration-time curve

from time of dosing extrapolated to infinity (AUC_(0- ∞)), time to reach maximum drug concentration (t_{max}), terminal elimination rate constant (λ_z), terminal elimination half-life (t½), systemic clearance (CL), and volume of distribution (Vd).

4.5 Secondary Endpoints

- Objective response rate, (ORR), defined as the percentage of subjects having complete response (CR) or partial response (PR), as determined by radiographic disease assessments per RECIST 1.1.
- Disease control rate (DCR) will include subjects that have best overall response (BOR) of CR, PR and stable disease (SD) for at least 12 weeks.
- Progression-free survival (PFS), defined as the interval from the date of first dose of investigational agent until the earliest date of disease progression (PD), as determined by investigator assessment of objective radiographic disease assessments per RECIST 1.1, or death due to any cause if occurring sooner than progression.
- Duration of response, (DOR), defined as the interval from the date measurement criteria are met for CR or PR (whichever is first recorded) until the earliest date of disease progression, as determined by investigator assessment of objective radiographic disease assessments per RECIST 1.1, or death due to any cause if occurring sooner than progression. Only subjects who achieve an initial response will be evaluated for DOR.
- Overall survival (OS), defined as the interval from the date of first dose of investigational agent until the date of death.
- The pharmacologically active dose of AGEN1884, determined through clinical signs of drug activity, surrogate markers, or pharmacodynamic studies, including but not limited to the presence of immune-related adverse events.

4.6 Exploratory Endpoints

• Other biomarker effects and outcome predictors for AGEN1884 in peripheral blood and/or tumor tissue will be evaluated as exploratory analyses.

5 PLANNED ANALYSIS

5.1 Summary of Changes to the Planned Statistical Analysis Described in the Protocol

None.

Confidential Page 12 of 30

5.2 Interim Analyses and Data Monitoring

No formal interim analyses are planned. Draft and interim data will be reviewed on a rolling basis to inform study progress.

5.3 Final Analysis and Reporting

A separate final analysis will be performed on Phase 1 and Phase 2 data. All final planned analyses per protocol and this analysis plan must be performed after either locking records for relevant subjects or visits included in the analysis or the full database lock. See Section 8 for discussion of requirements for data freeze, locking, and source data verification in the context of COVID-19 pandemic.

6 DEFINITIONS AND CONVENTIONS FOR DATA HANDLING

6.1 Definition of Baseline

For all evaluations, unless otherwise noted, baseline is defined as the most recent non-missing measurement prior to the first administration of study drug.

6.2 Definition of Study Days

Unless otherwise noted, study days of an evaluation are defined as the number of days relative to the first dose date which is designated as Day 1, and the preceding day is Day -1, the day before that is Day -2, etc.

Study days are calculated as

- (Date of assessment first dose date + 1) for assessments on/after first dose date
- (Date of assessment first dose date) for assessments before first dose date

6.3 Definition of On-Treatment Period

An on-treatment period is defined as the time from the first dose of study treatment until the end of treatment safety follow-up (4 weeks \pm 7 days from the last dose of study drug, i.e., until 35 days from the last dose) or end of the study, whichever occurs first.

6.4 Definition of an Extended On-Treatment Period

An extended on-treatment period (follow-up) is defined as the time from the first dose of study treatment through 90 days after the last dose of study treatment or end of the study, whichever

occurs first. This is used for reporting immune-related AEs and cluster terms and also as a sensitivity analysis for reporting all treatment-emergent adverse events.

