5.1.4 Final Safety Visit

The mandatory Safety Follow-Up Visit should be conducted for all subjects approximately 90 days after the last dose of study drug or before the initiation of a new antineoplastic treatment, whichever comes first. Subjects with an AE of Grade >1 will be further followed until the resolution of the AE to Grade 0-1 or until beginning of a new antineoplastic therapy, whichever occurs first. Subjects with an ADR ongoing at the Safety Follow-up Visit must be followed up until the ADR resolves, becomes stable, or is considered not clinically significant by the investigator.

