5.8.6.2 Recording and Reporting

5.8.6.2.1 Adverse Events

Subjects will be assessed for any AEs (non-serious or serious) from the date of consent until 90 days after the last study treatment. Any non-serious AEs identified during this time period will be followed until resolution or stabilization or only until the discontinuation from the study evaluation period if the event is not resolved at the conclusion of the study. The dates of onset and resolution for each AE will be recorded in the subject file. All AEs will be evaluated for duration, intensity, and attribution (relationship) to the investigational agent(s). All AEs (serious and non-serious) and laboratory abnormalities should be assessed for significance by the investigator, with consideration for the subject's overall medical history and concomitant medication profile.

If there is a change from baseline in a laboratory value, physical examination finding, vital sign, or medical finding, and the change is considered by the investigator to be clinically significant, the event must be recorded as an AE.

All AEs regardless of causality or seriousness must be recorded on the electronic case report form (eCRF). The frequency, grade, and nature of irAEs must be recorded.

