8.6.2 Adverse Events

Adverse events (AEs) will be coded using MedDRA version 22.1 and will be classified by SOC and PT.

Severity of AEs will be assessed by investigators according to the National Cancer Institute (NCI) Common Terminology Criteria for Adverse Events (CTCAE) Version 5, and AEs will be classified by investigators as either related or not related to the study drug. If the AE is reported as "Possible Related", "Probable Related", or "Highly Probable/Definite Related" in the eCRF, it will be considered as related; if it is reported as "Unrelated" or "Unlikely Related", it will be considered as unrelated.

Pre-existing conditions are those that started before and continued after signing of informed consent. Prior AEs (not treatment-emergent) are those occurring after the subject signed the informed consent and before the administration of the first dose of study treatment. Immune-related AEs will be evaluated in the extended on-treatment period to account for late toxicities. A separate listing will be provided for AEs incurred after on-treatment period.

Unless otherwise specified, TEAEs are AEs with onset during or after administration of first dose, or the worsening of a pre-existing condition during the on-treatment period. Immune-related AEs will be considered TEAEs during the extended on-treatment period. In a sensitivity analysis, TEAEs will be defined as AEs with onset during or after administration of first dose, or the worsening of a pre-existing condition during the extended on-treatment period. A separate listing will be provided of all AEs with onset date, or worsening date between end of "On-treatment period" (35 days) and end of "Extended on-treatment period" (90 days).

Any missing onset date, causality, or severity must be queried for resolution. Unresolved/missing causality and severity will be handled according to the following rules:

- An unresolved causality will be considered treatment-related
- An unresolved severity will be identified as an unknown severity

AEs with partial dates will be considered TEAEs unless the AE can unequivocally be determined as not treatment-emergent.

The following AEs are considered as AEs of special interest (AESIs):

- Infusion-related reactions per definition in NCI-CTCAE version 5 specification (per investigator assessment)
- Any elevated liver function test by investigators
- Any AE suspected to be immune-mediated (i.e. an irAE) by investigators

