8.7.6 Progression-Free Survival

Progression-free survival (PFS) is defined as the interval from the date of first dose of investigational agent until the earliest date of PD per RECIST 1.1 or death due to any cause within 90 days (i.e., 12 weeks+6 days) of last tumor assessment (if no progression is documented). If a patient transitioned to a new anti-cancer therapy, any time point assessment(s) and death(s) that happened after that will be disregarded.

The primary analysis will be performed ignoring transient PDs, using the same definition of transient PDs as in Section 8.7.1. Thus, the terminating event will be a non-transient PD or death, whichever occurs first. Patients who did not experience a non-transient PD or death will be censored on the date of last evaluable tumor assessment, the date of the last evaluable assessment without any assessment in the following 90 days and then followed by PD or death, or the last evaluable assessment performed before initiation of new anti-cancer therapy (if applicable), whichever comes earlier.

The alternative (sensitivity) analysis will be performed for terminating event of death or first observed time-point PD, whichever occurs first. Censoring will be on the date of last evaluable tumor assessment, the date of the last evaluable assessment without any assessment in the following 90 days and then followed by PD or death, or the last evaluable assessment performed before initiation of new anti-cancer therapy (if applicable), whichever occurs first.

PFS will be reported in months. Median PFS will be provided (estimated using K-M estimate, with 95% CI) and Kaplan-Meier curves of PFS will be plotted.

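### The SAP's 90-day adverse-event window does not stop when a new anti-cancer therapy starts, so AEs of the next therapy can enter the all-cause TEAE sensitivity analysis and the immune-mediated cluster tables

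*SAP*

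**What the plan says.** SAP 6.3 closes the on-treatment period "until 35 days from the last dose) or end of the study, whichever occurs first". SAP 6.4 lets the extended period run for "the time from the first dose of study treatment through 90 days after the last dose of study treatment", or to end of study if sooner, and gives its purpose: "This is used for reporting immune-related AEs and cluster terms and also as a sensitivity analysis for reporting all treatment-emergent adverse events".

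Under SAP 8.6.2, "TEAEs are AEs with onset during or after administration of first dose, or the worsening of a pre-existing condition during the on-treatment period"; the sensitivity version substitutes the extended period. Clusters are lists of MedDRA preferred terms evaluated in the extended period. For each, the SAP summarises incidence, grade, steroid and hormone treatment, and duration. Unresolved cluster AEs are censored at the end of the extended period.

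Protocol 5.8.6.2.1 states: "Subjects will be assessed for any AEs (non-serious or serious) from the date of consent until 90 days after the last study treatment". It also requires every AE to be recorded whatever its cause. Protocol 5.1.4 sets the last safety visit at "approximately 90 days after the last dose of study drug or before the initiation of a new antineoplastic treatment, whichever comes first". It ends follow-up of AEs above Grade 1 at the start of new therapy, but continues it for ongoing adverse drug reactions.

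For PFS, SAP 8.7.6 says: "If a patient transitioned to a new anti-cancer therapy, any time point assessment(s) and death(s) that happened after that will be disregarded". DOR (8.7.2) has the same rule, and BOR (8.7.1) uses only assessments before new therapy. OS (8.7.7) has no such rule.

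**The concern.** Safety is a primary endpoint and there is no control arm, so whatever falls in an AGEN1884 safety table is read as the AGEN1884 profile. Subjects with advanced cancer who progress may move to another therapy within 90 days of their last dose. The trial itself accepts short gaps between lines: Protocol 3.2.2, criterion 7c, describes entry 2 to 6 weeks after a PD-1/PD-L1 inhibitor, or sooner if it was well tolerated. That is an entry rule, not a switching rate, but it makes early switching plausible.

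If the window stays open after a switch, two things can go wrong. Toxicity of the next therapy can raise incidence, grade, steroid use and duration in tables that do not ask about cause. Alternatively, a site that stops safety follow-up at the switch leaves window time in which nothing is observed, while the analysis treats that time as observed.

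**Working it through.** The documents give no figure to reproduce: the trial is descriptive and states no switching rate.

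**1. Does anything else close the window?** Only end of study could. New therapy is not among the study-discontinuation reasons in Protocol 3.6, and Protocol 5.1.5 keeps following subjects for the start of another therapy. SAP 8.6.2 does not mention new therapy. The window therefore stays open.

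**2. A worked case.** Four doses at 3-week intervals put the last on Day 64. Suppose progression, new immunotherapy on Day 100, and diarrhoea judged unrelated to AGEN1884 on Day 130.
- 130 − 64 = 66 days after last dose. This is beyond 35, so outside the primary TEAE period, but within 90, so inside the extended period.
- If recorded, it counts in the TEAE sensitivity analysis and, by preferred term, in the diarrhea cluster.
- It does not count in the drug-related tables or, unless the investigator reports it as an irAE, in the primary irAE tables.

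**3. Share of window time.** Days on the next therapy for a switch s days after last dose are max(0, W − s), with W = 90 or 35.
- W = 90: s = 14 gives 76/90 = 84%; s = 28 gives 62/90 = 69%; s = 42 gives 48/90 = 53%; s = 60 gives 30/90 = 33%.
- W = 35: s = 14 gives 21/35 = 60%; s = 28 gives 7/35 = 20%; s of 35 or more gives 0.

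Assume switches are uniform on Days 28 to 90. The mean overlap per switcher is (90 − 28)/2 = 31 days.

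| Subjects switching (assumed) | Mean days per subject | Share of 90 post-dose days | Share of 154 days (64 + 90) |
|---|---|---|---|
| 30% | 9.3 | 10% | 6% |
| 50% | 15.5 | 17% | 10% |
| 70% | 21.7 | 24% | 14% |

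For the 35-day window under the same assumption, 7/62 = 11% of switchers start inside it, with a mean overlap of 3.5 days. The share is 0.30 × (7/62) × 3.5/35 = 0.3%, and likewise 0.6% and 0.8% for 50% and 70%.

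**4. Incidence.** One misattributed subject moves an incidence by 100/20 = 5.0 points among about 20 HCC subjects, 100/40 = 2.5 among about 40 non-HCC subjects, and 100/60 = 1.7 among 60. A ceiling on added cluster incidence is q × r, where q is the share who switch in the window and r the risk of a cluster-term AE from the next therapy. With q of 20% to 60% and r of 10% to 30%, both assumed, this runs from 2 to 18 points. It is a ceiling because it supposes that every such event is recorded and falls in a subject not already counted.

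**5. Duration.** Suppose follow-up of an unresolved cluster AE stops at a switch 40 days after last dose. The SAP censors it at Day 90, so 90 − 40 = 50 unobserved days count as ongoing AE. The subject stays in the risk set with no chance of a recorded resolution, which can raise the Kaplan-Meier median. This needs no event after the switch. Ongoing adverse drug reactions (Protocol 5.1.4) and SAEs (5.8.6.2.2) are followed further and are less affected.

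**6. Partial dates.** SAP 6.6 imputes an AE onset with missing day to the first of the month (or to first dose, in the month of treatment). SAP 6.7 imputes a post-study anti-cancer start with missing day to the last of the month, or to that medication's end date if earlier. When both fall in one month, the AE is placed before the switch, so a cut-off needs an explicit ordering rule.

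**The case against.** The strongest reply is that the tables closest to the primary endpoint are not exposed. That endpoint concerns drug-related AEs (SAP 4.4), and the drug-related tables use investigator causality. The primary irAE analysis is investigator-reported, and Protocol 5.8.6.1.2 requires other causes to be ruled out first. SAP 8.6.2 labels the cluster-based irAE definition exploratory. This stands, with one small gap: unresolved causality is counted as related.

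A reader might infer that next-therapy toxicity will be tabulated as AGEN1884 toxicity. The text supports only that it can be, if recorded. Protocol 5.1.4 puts the last safety visit before the switch, so capture afterwards may be limited.

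A reader might also infer that the 35-day window is equally at fault, or that every efficacy rule cuts at new therapy. Neither holds. The 35-day share is under 1% on the assumption above, and OS has no such cut. The BOR, DOR and PFS rules show that the date is usable; they do not oblige safety data to be cut.

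The SAP separately lists AEs arising between 35 and 90 days, and Protocol 5.8.5 records concomitant medication to 90 days, so late events are open to review. But the listing is not stated to flag new therapy, and it does not alter the tables.

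Finally, the 90-day window exists to catch late toxicity, and a plain truncation would lose some. That is a fair objection to a bare cut-off and is met by the retention rule under the fix.

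**Conclusion.** The concern holds in limited form. The 90-day window lacks a stop at new therapy. This leaves the all-cause TEAE sensitivity analysis and the preferred-term cluster tables open to AEs of the next therapy, and it can lengthen cluster AE durations through late censoring. Protocol 5.1.4 and 5.8.6.2.1 add to this, because sites can collect different data for the same window.

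The 10%, 17% and 24% are shares of post-dose time under assumed switch rates and timing. It is tempting to read them as inflation of incidence. The documents give neither switch rates nor event rates for later therapies, so no inflation figure can be derived; the 2-to-18-point ceiling rests wholly on assumptions. The firm figure is the step per misattributed subject: 5.0 points in 20, 1.7 in 60. The change should be made because it is cheap and the affected tables describe the immune-mediated profile. The drug-related and primary irAE tables are not seriously threatened.

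**What to change.** - For the all-cause 90-day TEAE and cluster tables, end the window at the earliest of 90 days after last dose, end of study, or the day before new systemic anti-cancer therapy. Keep later AEs that the investigator judges related to AGEN1884 or reports as irAEs, and list the others separately. An acceptable alternative is to flag events after the switch and show these tables with and without them.
- Censor unresolved cluster AE durations at the same date, or at last AE follow-up if earlier.
- State how partial AE onset dates and partial new-therapy start dates are ordered.
- Reconcile Protocol 5.1.4 with 5.8.6.2.1 on AE collection after new therapy starts.

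The cost is SAP wording and modest programming, plus protocol wording for the last item. The start of new therapy is already followed (Protocol 5.1.5), has imputation rules (SAP 6.7) and already cuts BOR, DOR and PFS. The small downside is that a late event truly caused by AGEN1884 but judged unrelated moves from the table to the listing; showing both versions avoids that.
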